Primary Objective: Define anaphylaxis rates in OFCs for peanut allergy halted by TEWL stopping rules plus standard of care clinical assessment versus control OFCs, where challenges are halted based only on clinical assessment of reaction status per standard of care.

Secondary Objectives:

1. Define overall allergic reaction rates in peanut OFCs halted by TEWL stopping rules versus usual care.
2. Define anaphylaxis likelihood and severity via Brighton and CoFAR criteria among anaphylaxis reactions in peanut OFCs halted by TEWL stopping rules versus usual care.

2. Specific Aims

Aim 1: Determine the ability of TEWL-based stopping rules to impact OFC safety features for peanut OFCs.

Sub-aim 1: Define anaphylaxis occurrence rate in OFCs halted by TEWL stopping rules versus usual care OFCs, where challenges are halted based solely on clinical assessment of reaction status.

Sub-aim 2: Define anaphylaxis likelihood and severity via Brighton and CoFAR criteria among anaphylaxis reactions in OFCs halted by TEWL stopping rules versus usual care.

Sub-aim 3: Define overall allergic reaction rates in OFCs halted by TEWL stopping rules versus usual care.

Table 1

OBJECTIVES	ENDPOINTS	JUSTIFICATION FOR ENDPOINTS
Primary Define anaphylaxis rates in OFCs for peanut allergy halted by TEWL stopping rules versus usual care OFCs, where challenges are halted based on clinical assessment of reaction status.	Anaphylaxis occurrence rate	Anaphylaxis is the key adverse clinical outcome of “positive” OFCs and thus a major safety issue of OFCs. If TEWL can reduce anaphylaxis rate while still maintaining overall peanut allergy diagnosis accuracy, this methodology will have utility.
Secondary Define overall allergic reaction rates in peanut OFCs halted by TEWL stopping rules versus usual care.	Secondary endpoints will include anaphylaxis severity and overall reaction rates.	Anaphylaxis severity is a key safety question in OFCs. If anaphylaxis severity

OBJECTIVES	ENDPOINTS	JUSTIFICATION FOR ENDPOINTS

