Define anaphylaxis likelihood and severity via Brighton and CoFAR criteria among anaphylaxis reactions in peanut OFCs halted by TEWL stopping rules versus usual care.	Anaphylaxis likelihood will be defined by the Brighton criteria. Anaphylaxis severity will be defined via the modified CoFAR criteria (these are defined later in the protocol).	is impacted by TEWL stopping rules, that would be valuable information. Overall allergy reaction rates are important to understand non-anaphylaxis events within OFCs. Many OFCs are stopped based on a non-anaphylactic allergic reaction (i.e., isolated hives without other symptoms) per standard of care. Such non-anaphylactic events are safer than anaphylaxis by definition, so if anaphylaxis events without TEWL stopping rules are converted to non-anaphylactic reactions, that would be a very useful data-point because we would be preserving the accuracy of the OFC via standard of care while reducing the risk by avoiding anaphylaxis.
Tertiary/Exploratory		
Define descriptive characteristics of allergy reactions/anaphylaxis among peanut OFCs wherein TEWL stopping rules are or are not used.	Exploratory endpoints may include but are not limited to time to first treatment, time to first symptom, epinephrine use, any medication use, and time to meeting a TEWL-based stopping rule.	These additional endpoints provide useful safety and descriptive features that may help define larger clinical trials with this TEWL modality in the future.

3. Background

Food allergy (FA) presents a major societal health burden because it impacts over 5 million (8%) children in the United States (US) and grows more common every year ¹⁻³. FA causes food anaphylaxis, a deadly, systemic allergic reaction causing over 200,000 US emergency room visits per year ⁴⁻⁶. FA also causes childhood nutritional and growth deficiencies ⁷⁻¹⁰, severe anxiety for patients and caregivers ¹¹⁻¹³, and high healthcare and family costs due to the need for epinephrine auto-injectors, healthcare visits, and food avoidance ¹⁴⁻¹⁸. An accurate diagnosis is therefore crucial to avoiding a “disaster of misdiagnosis” where the consequences of perceived FA are realized due to false positive testing in the absence of true disease ^{7,19}.

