Participants will be randomized 1:1 to the intervention and control groups. We will use permuted block randomization. We will vary the block size from 2 to 4 in order to enhance blinding. We will upload a 40-person participant list to randomization software that will produce the randomization, which will be performed at visit 1 (initial screening visit) or no later than the day of the research food challenge. The TEWL study coordinator will learn the group designation for each participant at the start of that participant's challenge by the software.

TEWL measurement methods.

All subjects will undergo continuous TEWL measurement ^{48,54}. We will use a Tewameter VT310 device (Khazaka, Germany); these probes and supporting software were supplied at no cost and with no obligation except mention of material support in publications by the manufacturer. Measurements are taken using a small adhesive to attach the probe to the skin. Measurements are taken on the volar forearm. Data are collected in MPA CT Plus software (Khazaka, Germany) which provides note-taking functions and exports data into Microsoft Excel (Seattle, WA) for analysis.

Adjudication of OFC results.

A FA physician will adjudicate reactions and diagnose anaphylaxis identically to usual care in the FA clinic. The Brighton anaphylaxis likelihood scale will be used to assess anaphylaxis likelihood. The decision tree is copied here (next page, Figure 3). The CoFAR anaphylaxis severity scale will be used for anaphylaxis severity⁷¹ and is below in the adverse event grading section of the protocol. The Brighton score gives a 0-3 score of anaphylaxis likelihood (0 = no anaphylaxis, 3 = highly likely). The CoFAR severity score gives a grade of 1-5 of anaphylaxis severity (where 1 = mild, 5 = death).

Any symptom typical of food allergy (see Brighton and CoFAR scales) will count as a reaction, consistent with standard of care diagnosis for peanut allergy. Note that this is distinct from anaphylaxis.

TEWL-based stopping rules will be applied to the intervention group. We plan to use a 1 g/m²/h increase in TEWL value averaged over the 2 minute period after a fully-consumed food dose versus the 2 minute period averaged over the period just prior to that food dose. If the individual meets this threshold, at the first sign of a clinical symptom, the food challenge will be stopped.

[figure not shown]

Figure 3: Brighton Anaphylaxis Likelihood Scale

PrePARE Trial v2.2, 30 November 2022

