Treatment of reactions.

Reaction treatment will be based on symptoms assessed by the allergist per the clinical standard of care. If the participant meets anaphylaxis criteria ⁷¹, then weight-based anaphylaxis epinephrine dosing will be given, with a follow-up dose 5 minutes later if symptoms do not resolve. Albuterol via nebulizer or inhaler/mask (depending on age) and liquid diphenhydramine and cetirizine (both are antihistamines and use weight-based dosing) will be available and used after epinephrine in the case of anaphylaxis. All doses will be calculated prior to the challenge. If a participant has a reaction not meeting anaphylaxis criteria (i.e., they only have hives but no additional symptoms), the physician may choose to stop the OFC and give an antihistamine. If the TEWL-based stopping rule is invoked, the OFC will be stopped (no more food doses given); if the participant meets anaphylaxis criteria at that time, epinephrine will be given, otherwise an antihistamine dose will be given per standard of care.

Table 2: Outcome measures		Definition
Primary outcome	Anaphylaxis rate	Any Brighton Level 1, 2, or 3 anaphylaxis (see table above)
Secondary outcomes	Reaction rate	Any objective symptom of allergic reaction occurs (e.g., hives, angioedema, vomiting, wheeze, etc) not rising to the definition of anaphylaxis.
	Anaphylaxis severity	CoFAR score, defined below
	Anaphylaxis likelihood	Brighton score, defined above
Exploratory endpoints (Partial list)	Time to first symptom	Time from first food dose to any symptom
	Reaction symptoms	All reaction symptoms listed
	Epinephrine use	Any epinephrine administration
	Any medication use	Any medication administration
	Time to stopping rule	Time in minutes to stopping rule trigger

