Outcome measures. The outcome measures collected for each group in Table 2 show the hypothesized relationship for each group. If a stopping rule is implemented, that will be considered a positive challenge. We hypothesize that the intervention group will have lower anaphylaxis rates and/or severity via earlier OFC stoppage and earlier time to or more frequent treatment with non-epinephrine medications (such as antihistamines). We suspect the overall reaction rate will remain the same, but that these reactions will not devolve into anaphylaxis in the intervention group due to the above factors. Anaphylaxis will be defined according to current practice parameters ⁷², which is broadly considered to be at least two symptoms consistent with allergic reactions (cutaneous, gastrointestinal, respiratory, elevated heart rate, among others) or a decrease in blood pressure.

Post-OFC

1. Participants without evidence of an allergic reaction during the OFC will receive a follow-up phone call 1 day after the OFC to follow up on any additional symptoms or concerns.

2. Participants that had a reaction will be scheduled for a follow-up call within 1 day of the OFC to assess for additional symptoms or resolution of symptoms per the standard of care.

c. Subject Withdrawal

- i. Under what conditions will a subject be withdrawn prior to completion
- ii. If a subject withdraws prior to completion, what is the plan for the use of their data

Any subject may withdraw at any time for any reason. These reasons may include but are not limited to:

- Subject's request, no reason needed
- Adverse event – at Investigator's request. Potential examples include concern that proceeding further would impose unanticipated risk not otherwise delineated here or for any reason that continued participation could impact study integrity.

The data for any subject who withdraws prior to completion will be flagged as incomplete data in our data set. We will delete data if the subject requests this.

d. Data Retention and/or Data Destruction Plan

- i. How long will you keep subject data?
- ii. If you plan to destroy the data, how will you destroy it?

Data collected will be retained for study record keeping purposes and for future research use for up to 5 years or in accordance with our sponsor's policies. Thereafter, data will be fully de-identified fully and retained indefinitely. No data will be destroyed.

Risks & Benefits

- a. What are the risks and what will be done to monitor the risks?

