We will report any adverse events and other reportable incidences and occurrences (ORIO) to the IRB. Any adverse event or ORIO will be documented of that event including a description, subject number, date, outcome, and follow-up. Reporting of adverse events and ORIOs will follow IRBMED's reporting timetable and will occur at least yearly.

Statistical Design

Stopping rules. The anaphylaxis prediction threshold used in the study 2 trial will be data-driven based on results from our ongoing data collection study. We will perform a series of logistic regression models testing the predictive value of various levels of absolute increases in TEWL, thresholds of TEWL and their combinations. These will be tested against time to first symptom, time to formal anaphylaxis diagnosis, time to first medication use, and time to epinephrine use. To avoid overfitting, these analyses will use a 2:1 derivation: validation random split. Corrections will include baseline TEWL value and variance. A minimum sustained timespan meeting the threshold (such as 30-60 seconds) may be needed to minimize the effects of noise in the measurement.

Endpoints. The primary endpoint will be anaphylaxis rate among the intervention group versus the control group and will be reported with a 95% confidence interval. Secondary endpoints will include anaphylaxis severity and overall reaction rates. Exploratory endpoints may include but are not limited to time to first treatment, time to first symptom, epinephrine use, any medication use, and time to meeting a stopping rule (regardless of whether it was implemented); all will be reported with 95% confidence intervals. Exact p-values will be calculated using Fischer's test.

Descriptive analyses. Descriptive analyses will be reported. Continuous baseline measures will be reported using either mean (or geometric mean) with 95% confidence interval or median with first and third quartiles, as appropriate. Categorical baseline and demographic characteristics and study disposition will be reported as frequencies and proportions.

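### Table 2's only reaction row leaves out anaphylaxis, so it does not measure the overall reaction rate named in secondary objective 1

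*Combined protocol and SAP*

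**What the plan says.** The combined protocol and SAP describes this endpoint in several places.

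- **Synopsis and section 1 (Objective), secondary objective 1:** "Define overall allergic reaction rates in peanut OFCs halted by TEWL stopping rules versus usual care".
- **Statistical Design, Endpoints:** "Secondary endpoints will include anaphylaxis severity and overall reaction rates".
- **Outcome measures paragraph after Table 2:** "We suspect the overall reaction rate will remain the same, but that these reactions will not devolve into anaphylaxis in the intervention group".
- **Table 2, secondary outcome Reaction rate:** "Any objective symptom of allergic reaction occurs (e.g., hives, angioedema, vomiting, wheeze, etc) not rising to the definition of anaphylaxis".
- **Table 1, justification for the secondary endpoints:** "Overall allergy reaction rates are important to understand non-anaphylaxis events within OFCs", followed by "Many OFCs are stopped based on a non-anaphylactic allergic reaction (i.e., isolated hives without other symptoms) per standard of care". It goes on to say that turning anaphylaxis into milder reactions would be useful to observe.
- **Adjudication of OFC results:** "Any symptom typical of food allergy (see Brighton and CoFAR scales) will count as a reaction", and then "Note that this is distinct from anaphylaxis".

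Table 2 is the only place where the outcomes are tabulated with definitions. It has no row for reactions of every kind taken together.

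**The concern.** An analyst who follows Table 2 will report a rate that leaves out every child with anaphylaxis. A reader who starts from secondary objective 1 will expect a rate that includes them. In a successful trial the two move differently. The inclusive rate should stay level, as the Outcome measures paragraph expects, while the Table 2 rate should go up.

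The choice matters for interpretation. Table 1 says the method is useful if it lowers anaphylaxis and the challenge still diagnoses peanut allergy accurately. Whether as many children still react in both arms bears on that, and the Table 2 rate alone cannot show it. With the text as it stands, the same data could be summarised as reactions unchanged or as reactions increased, depending on which section is followed.

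**Working it through.** **Inputs.** Planned anaphylaxis rates are 80% (control) and 30% (intervention), with 19 per group needed and 20 enrolled (Population size). An estimated 20% of both groups pass the challenge (benefits to the individual), so 100% - 20% = 80% react in each arm.

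**The plan's own figure.** The normal-approximation sample size for 80% versus 30%, two-sided alpha 0.05 and 80% power, is 15 per group without and 19 with continuity correction. Exact enumeration of Fisher's test gives 83.5% power at 18 per group and 85.2% at 19. The stated 38 is therefore reproduced, and 38 / 0.95 = 40. This calculation concerns anaphylaxis only and does not use the reaction rate.

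**The identity.** With one definition of anaphylaxis and one symptom standard, in each arm:

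non-anaphylactic rate = overall rate - anaphylaxis rate.

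Let R be the overall rate, the same in both arms. Then, intervention minus control:

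(R - 0.30) - (R - 0.80) = +0.50.

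R cancels, so the Table 2 rate rises by 50 points whatever the common overall rate is. If the Table 2 rate stayed level while anaphylaxis fell by 50 points, overall reactions would also have to fall by 50 points. That contradicts the Outcome measures paragraph.

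**What the two rates would look like with 20 per arm** (Newcombe 95% CI, intervention minus control, in percentage points):

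| Common overall rate | Table 2 rate, control vs intervention | CI, Table 2 rate | CI, inclusive rate |
|---|---|---|---|
| 80% (from the 20% pass rate) | 0% vs 50% | +24 to +70 | -25 to +25 |
| 90% (assumed) | 10% vs 60% | +21 to +70 | -21 to +21 |
| 100% (assumed) | 20% vs 70% | +19 to +70 | -16 to +16 |

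The first row is a limiting case. Combining the plan's pass rate with its control anaphylaxis rate leaves no control child with a milder reaction. That sits badly with Table 1's remark that many challenges stop for one. The 50-point shift does not depend on that row.

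**Check of the inclusive interval at 16/20 in each arm.** The Wilson limits for 16/20 are 0.584 and 0.919. The half-width is sqrt((0.800 - 0.584)^2 + (0.919 - 0.800)^2) = sqrt(0.0467 + 0.0142) = 0.247, or about 25 points either way.

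**The case against.** The exclusive definition has support in the plan. Table 1 ties the overall rates to understanding events short of anaphylaxis and says that conversion of anaphylaxis to milder reactions is worth seeing. The Table 2 row measures that conversion, and a rise in it is what the investigators hope for. The adjudication section's remark that a reaction is distinct from anaphylaxis can be read the same way, though it can also mean only that not every reaction is anaphylaxis. The expectation of no change is introduced as a suspicion and is not an outcome definition. The row states its exclusion plainly, and the overall rate can be rebuilt by adding the anaphylaxis and reaction rows, given consistent definitions. No decision rule or margin rests on this secondary endpoint in a 40-child pilot.

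Much of this stands. It shows that the row is worth keeping and that the practical harm is limited. It does not remove the inconsistency: the Outcome measures paragraph cannot hold under the Table 2 definition if anaphylaxis falls, and nothing in the plan says that the two rows are to be added.

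A reader might infer more than the documents support, in three ways.

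- **That a higher Table 2 rate would be a false signal of harm.** It would be a true count of milder reactions. The risk lies in reading it as the overall rate.
- **That secondary objective 1 can only mean the inclusive rate.** The word overall and the no-change expectation point that way, but Table 1 pulls the other way. What is established is that two meanings are in use.
- **That the primary result is put in doubt by this point.** It is not. Table 2 uses Brighton levels for anaphylaxis and the Outcome measures paragraph uses practice parameters. That difference bears on the primary outcome and should be raised separately. The Brighton decision tree is not visible in the available text, so how far the two diverge cannot be judged here.

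**Conclusion.** The point holds as an inconsistency in a named secondary endpoint and should be fixed before the arms are compared. Table 2 as written does not give the rate that the Outcome measures paragraph describes. At the planned anaphylaxis rates the two versions differ by 50 points in the between-arm comparison: +50 for the Table 2 rate and 0 for the inclusive rate. This assumes equal overall reactions in both arms, one definition of anaphylaxis and one symptom standard. A smaller fall in anaphylaxis gives a correspondingly smaller gap.

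The symptom standard is part of this point because it decides whether the rows add up. The adjudication section counts any typical symptom, whereas Table 2 requires an objective one. The consequence is confined to how secondary objective 1 is reported and read.

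**What to change.** In Table 2:

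1. Add a secondary outcome, overall reaction rate, defined as any allergic reaction including anaphylaxis, and name it as the outcome for secondary objective 1.
2. Relabel the existing row as the non-anaphylactic reaction rate and keep it as a separate outcome for the conversion question in Table 1.
3. State one symptom standard, either any symptom or objective symptoms only, and apply it to both rows and to the adjudication section.

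In the Statistical Design section, use the same two names and report the between-arm difference in the overall rate with its 95% CI, descriptively. The plan sets no equivalence margin, and an interval of about 25 points either way cannot establish that the rates are the same.

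The cost is one row added, one row relabelled and a sentence on the symptom standard. No new data are needed, and the primary outcome and the 40 participants are unchanged.

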Objectives: Primary Objective: *Define anaphylaxis rates in OFCs for peanut allergy halted by TEWL stopping rules plus standard of care clinical assessment versus control OFCs, where challenges are halted based only on clinical assessment of reaction status per standard of care.*

Secondary Objectives:

1. Define overall allergic reaction rates in peanut OFCs halted by TEWL stopping rules versus usual care.
2. Define anaphylaxis likelihood and severity via Brighton and CoFAR criteria among anaphylaxis reactions in peanut OFCs halted by TEWL stopping rules versus usual care.

Endpoints: Primary Endpoint: Anaphylaxis occurrence rate

Secondary Endpoints: Secondary endpoints will include anaphylaxis severity and overall allergic reaction rates.

Anaphylaxis likelihood will be defined by the Brighton criteria. Anaphylaxis severity will be defined via the modified CoFAR criteria (these are defined in the protocol).

Study Population: The total study population will be 40 individuals aged 6 months to 5 years, any gender, any demographic group, with a high likelihood of peanut allergy (defined in protocol). The study will take place in Michigan.

Phase: N/A

Description of Sites/Facilities This will be a single center study at the University of Michigan in Ann Arbor, MI.

[figure not shown]
Enrolling Participants:

Description of Study Intervention: This study will evaluate the use of transepidermal water loss (TEWL) continuous measurement during oral food challenge for food allergy (peanut). A stopping rule based on TEWL will be tested against usual oral food challenge care. In both cases, the standard of care will be used, where even a single symptom of an allergic reaction is used to stop oral food challenges. TEWL measures the rate of water loss from the skin in $\text{g}/\text{m}^2/\text{h}$ as a flux of water mass through an area over time.

Study Duration: 24 months

Participant Duration: Up to 9 days

Schema

Schedule of Activities

Procedures	Screening Day -7 to -1	OFC visit Visit 1, Day 1	Check-in Day 2	call,
Pre-screening questions	X			
Informed consent	X			
Confirm eligibility	X	X		
Demographics	X			
Medical history	X			
Randomization	X			
Administer study OFC		X		
Concomitant medication review	X			
Physical exam (including height and weight)		X		
Vital signs		X		
Weight		X		
Adverse event review and evaluation	X	X	X	
Complete Case Report Forms (CRFs)	X	X	X	

1. Objective

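### Table 2 leaves anaphylaxis out of the secondary outcome Reaction rate, while the plan's hypothesis for that rate holds only if anaphylaxis is counted

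*Combined protocol and SAP*

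**What the plan says.** The combined protocol and SAP describes this outcome in several places.

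- **Objective.** The first secondary objective (Synopsis and section 1) reads "Define overall allergic reaction rates in peanut OFCs halted by TEWL stopping rules versus usual care". The Endpoints paragraph of Statistical Design also lists overall reaction rates and gives no definition.
- **Definition.** Table 2 (section 5.b.iv), the only table that defines outcomes, gives Reaction rate as "Any objective symptom of allergic reaction occurs (e.g., hives, angioedema, vomiting, wheeze, etc) not rising to the definition of anaphylaxis". The row above it defines the primary outcome as Brighton Level 1, 2 or 3 anaphylaxis.
- **Hypothesis.** The Outcome measures paragraph, which refers to Table 2, states: "We suspect the overall reaction rate will remain the same, but that these reactions will not devolve into anaphylaxis in the intervention group".
- **Justification.** Table 1 wants the overall rate for what it shows about events short of anaphylaxis, and adds that "if anaphylaxis events without TEWL stopping rules are converted to non-anaphylactic reactions, that would be a very useful data-point".
- **Adjudication.** Adjudication of OFC results says "Any symptom typical of food allergy (see Brighton and CoFAR scales) will count as a reaction". Its next sentence notes that a reaction in this sense is a different thing from anaphylaxis.

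**The concern.** The hypothesis describes a fixed pool of reactions, fewer of which go on to anaphylaxis. A child who would have had anaphylaxis and instead has hives alone stays in that pool. Under Table 2 the same child is outside the count before conversion and inside it afterwards, so each conversion raises the rate. The outcome as defined therefore cannot test the hypothesis attached to it.

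The direction matters for interpretation. Table 1 sets a condition on the whole approach: "If TEWL can reduce anaphylaxis rate while still maintaining overall peanut allergy diagnosis accuracy, this methodology will have utility". An unchanged overall reaction rate would support that condition. A Table 2 rate that rises in the intervention arm could be misread as harm when it is the hoped-for effect. A Table 2 rate that is equal across arms while anaphylaxis falls could be read as reassurance, although total objective reactions would then have fallen.

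The symptom standard also differs: Adjudication counts any typical symptom, Table 2 only objective ones.

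**Working it through.** **Inputs**
- Pass rate 20% in both groups (Risks & Benefits, benefits to the individual), so an overall reaction rate R = 1 − 0.20 = 0.80 in each arm.
- Anaphylaxis rate A: 0.80 control, 0.30 intervention (Statistical Design, Population size).
- 20 per arm enrolled (same paragraph).

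**The plan's own figure.** The plan states no figure for the reaction rate. The anaphylaxis inputs do reproduce its sample size. With two-sided alpha 0.05 and 80% power, the normal-approximation formula gives

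n = [1.96·√(2·0.55·0.45) + 0.8416·√(0.8·0.2 + 0.3·0.7)]² / 0.5² = 14.3.

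The continuity correction gives (14.3/4)·[1 + √(1 + 4/(14.3·0.5))]² = 18.1, so 19 per group and 38 in total. Then 38/0.95 = 40. Exact enumeration of Fisher's test gives 85.2% power at 19 per group.

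**Reaction rate under each reading**

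The Table 2 rate is T = R − A. The inclusive rate is R.

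| Reading | Control | Intervention | Difference | Fisher p at expected counts |
|---|---|---|---|---|
| Table 2 (T) | 0.80 − 0.80 = 0, 0/20 | 0.80 − 0.30 = 0.50, 10/20 | +50 points | 0.0004 |
| Inclusive (R) | 0.80, 16/20 | 0.80, 16/20 | 0 | 1.00 |

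**Why the gap is 50 points.** T(int) − T(ctl) = [R(int) − R(ctl)] + [A(ctl) − A(int)]. With equal overall rates the first bracket is zero, and the Table 2 difference is the anaphylaxis difference with its sign reversed: 0.80 − 0.30 = 0.50. The p-value of 0.0004 is therefore not separate evidence of anything.

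**Sensitivity (assumed values)**
- Pass rate of 15%, 10%, 5% or 0% in both arms: Table 2 rates of 5% vs 55%, 10% vs 60%, 15% vs 65% or 20% vs 70%. The gap stays at 50 points.
- Weaker effect at a 20% pass rate: intervention anaphylaxis of 50% gives 0/20 vs 6/20 (p = 0.020); 60% gives 0/20 vs 4/20 (p = 0.106).
- Equal Table 2 rates: by the identity above, if T is equal and anaphylaxis falls by 50 points, R falls by 50 points, for example from 80% to 30%. This departs from the plan's equal pass rates and only illustrates how the figure could mislead.

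**Symptom standard.** The documents give no rate of subjective-only reactions. Each child classified differently moves an arm by 1/20 = 5 points.

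**The case against.** The best defence is that Table 2 is deliberate and governs. It alone has a definition column for this outcome. Table 1 ties the overall rate to events short of anaphylaxis, and the Adjudication paragraph separates a reaction from anaphylaxis. The hypothesis is loosely worded, and the word overall in the objective suggests inclusion without defining it. All of this stands. A reader might infer that the objective by itself requires anaphylaxis to be counted; the documents do not go that far. But if Table 2 governs, the hypothesis is wrong for the listed outcome, so some text has to change on either reading.

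The figures can also be questioned. The 0% joins an estimate from the benefits section to a power assumption, and together they imply that no control child has a milder reaction. Table 1 says that many challenges end that way, so an exact 0% is doubtful. That too stands.

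Finally, the consequence is limited. The anaphylaxis and reaction rows add up to the overall objective rate, provided both use the same definition of anaphylaxis, and all reaction symptoms are recorded. Being able to recover the figure does not settle which one was pre-specified.

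A reader might also infer a conflict in the stopping-rule text, because "If a stopping rule is implemented, that will be considered a positive challenge" seems to add a third notion of reaction and other paragraphs mention the rule without its symptom condition. The documents do not support this. The rule itself says "If the individual meets this threshold, at the first sign of a clinical symptom, the food challenge will be stopped", any typical symptom already counts as a reaction under Adjudication, the other mentions are shorthand for that rule, and diagnosis follows standard of care in both arms.

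**Conclusion.** The inconsistency is real, is in current text, and should be fixed. Followed as written, Table 2 yields a figure that cannot test the hypothesis stated for it and that rises when the intervention works. On the planning assumptions, expected control versus intervention rates are 0% versus 50% under Table 2 and 80% versus 80% with anaphylaxis included. The equal 80% rests on the 20% pass rate applying to both arms; the 50-point gap rests on equal overall rates and on the full planned effect.

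A reader might take 0% versus 50% as the result the trial will report, or as a second effect beside the primary one. It is neither: it is an expectation, and it restates the primary difference. Nor does the point reach the primary endpoint or the sample size. This is an unpowered secondary endpoint in a 40-child pilot.

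**What to change.** Split the Reaction rate row of Table 2 in two:

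- **(a) Overall reaction rate:** any allergic reaction, including anaphylaxis as defined for the primary outcome (Brighton Level 1-3). This is the secondary endpoint for the first secondary objective and for the hypothesis in Outcome measures.
- **(b) Non-anaphylactic reaction rate:** a reaction that does not meet that same definition, reported descriptively.

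State one symptom standard, any symptom or objective symptoms only, and use it in both Adjudication of OFC results and Table 2. Either can be defended; the choice belongs to the investigators. The wording on the stopping rule and on positive challenges can stay as it is.

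The cost is a few wording edits and one more rate to report, with no new procedures, participants or data.
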